## 8. ANALYSIS POPULATIONS

The following subject population will be used for disposition analyses:

- The Enrolled Population will consist of all subjects who have a signed informed consent or assent. If a subject is randomly assigned to a treatment, then treatment assignment will be based on randomized treatment; otherwise, they will be deemed a screen failure and will only appear in the overall summary columns of output.

The following subject population will be used for safety analyses:

- The Safety Population will consist of all subjects who receive at least 1 application of study treatment. Treatment assignment will be based on the treatment actually received. If a subject receives any amount of SB206, then they will be summarized in the SB206 10.3% QD arm.

The following subject populations will be used for efficacy analyses:

- The ITT Population will consist of all subjects who are randomized who have a signed informed consent or assent as applicable. Treatment assignment will be based on the randomized treatment.
- The Per-Protocol (PP) Population will consist of all subjects in the ITT Population who had no significant protocol deviations that impacted the analyses of efficacy endpoints. Final determination of subject inclusion in the PP Population will be made prior to unblinding. Treatment assignment will be based on the randomized treatment.

## 9. STUDY POPULATION

### 9.1 Subject Disposition

Subject disposition information will be summarized for all subjects by treatment group. Summaries will include: the number of subjects screened, the number of screen failures, the number of subjects in each analysis population, the number of subjects where study treatment stopped, primary reason for study treatment stopped, the number of subjects completing 12 weeks of the study (defined as having answered Yes to the question “Did the subject complete treatment through Week 12?” on the end of treatment eCRF page or an end of treatment reason of “Complete Clearance Confirmed by Investigator Prior to Week 12” and does not have a Study Exit date prior to the subject’s Week 12 visit date), the number of subjects completed the study, and the primary reason for discontinuation (including summaries for prior to Week 12 and overall).

A summary of the number of subjects in each center and each population will be presented.

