2.1.4.2 Clinical Safety

It should be noted some subjects have experienced transient asymptomatic erythema at the application site within 5 minutes of dosing, which typically lasted ≤ 15 minutes. This is due to nitric oxide's vasodilatory pharmacologic effect and is an expected event.

Summaries of the safety analyses of the phase 3 studies ([NI-MC301](#) and [302](#)) are ongoing, and the CSRs are under preparation. The treatment emergent adverse event (TEAE) profile of SB206 through the Week 24 was found to be favorable and was very similar between the two studies. Study drug discontinuations in the SB206 treatment arm were all due to application site reactions and no treatment-related serious adverse events were reported across both studies.

Table 2 Overall Summary of TEAEs (Safety Population) through Week 24

	NI-MC301		NI-MC302	
	Vehicle (n=116)	SB206 (n=235)	Vehicle (n=117)	SB206 (n=237)
Subjects who reported at least one TEAE	36 (31.0%)	115 (48.9%)	30 (25.6%)	120 (50.6%)
Serious TEAE	0	0	1 (0.9%)	1 (0.4%)
Treatment-related TEAE	19 (16.4%)	86 (36.6%)	8 (6.8%)	86 (36.3%)
TEAE leading to study drug discontinuation	1 (0.9%)	7 (3.0%)	1 (0.9%)	17 (7.2%)

The TEAEs reported in greater than 5% of subjects in the SB206 treated groups were application site pain and application site erythema, with the majority of these TEAEs being mild or moderate in severity.

Table 3 TEAEs in $\geq 2\%$ of subjects in either SB206 treated group or Vehicle group (NI-MC301)

	Vehicle (n=116)			SB206 (n=235)		
	Mild	Moderate	Severe	Mild	Moderate	Severe
Application site pain	8 (6.9%)	0	0	34 (14.5%)	16 (6.8%)	1 (0.4%)
Application site erythema	2 (1.7%)	1 (0.9%)	0	13 (5.5%)	15 (6.4%)	1 (0.4%)
Application site pruritus	0	0	0	8 (3.4%)	2 (0.9%)	1 (0.4%)
Pyrexia	3 (2.6%)	1 (0.9%)	0	7 (3.0%)	4 (1.7%)	0
Application site exfoliation	0	0	0	4 (1.7%)	5 (2.1%)	1 (0.4%)
Application site scar	9 (7.8%)	0	0	6 (2.6%)	0	0
Application site swelling	1 (0.9%)	0	0	5 (2.1%)	1 (0.4%)	0
Application site dermatitis	1 (0.9%)	0	0	1 (0.4%)	3 (1.3%)	1 (0.4%)
Application site discolouration	0	0	0	5 (2.1%)	0	0
Vomiting	1 (0.9%)	0	0	2 (0.9%)	5 (2.1%)	0
Upper respiratory tract infection	2 (1.7%)	0	0	3 (1.3%)	2 (0.9%)	0

Table 4 TEAEs in $\geq 2\%$ of subjects in either SB206 treated group or Vehicle group (NI-MC302)

[figure not shown]
	Vehicle (n=117)			SB206 (n=237)		
	mild	moderate	severe	mild	moderate	severe
Application site pain	1 (0.9%)	1 (0.9%)	0	15 (6.3%)	22 (9.3%)	0

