6.8 Discontinuation or Withdrawal

6.8.1 Individual Subjects

If at any time during the study the investigator determines that it is not in the best interest of the subject to continue treatment, the subject's treatment will be discontinued. The investigator can discontinue the treatment for a subject at any time if medically necessary. If a subject's treatment is permanently discontinued by the investigator because of an AE, that AE should be indicated as the reason for treatment discontinuation. In this case, the subject is discontinued from the treatment, but still participates in the study and the subject is encouraged to follow the visit schedule and complete all assessments, particularly those at Week 12 and 24.

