6.8.2.2 Permanent Discontinuation of Treatment

The investigator may discontinue a subject's treatment if the subject/caregiver has failed to follow study procedures or to keep follow-up appointments. Appropriate documentation in the subject's study record and the study database regarding the reason for treatment discontinuation must be completed. See Section [6.8.2](#) for additional details.

Reasons for an investigator's withdrawal of a subject **from the treatment** may include, but are not limited to, the following:

- Safety (e.g., severe adverse reactions, pregnancy)
- When a concomitant medication or treatment likely to interfere with the results of the study is reported, or required, by the subject, the investigator will decide, in consultation with the CRO whether the subject is to be withdrawn.

Reason(s) for discontinuation from the treatment as listed in the study record will be entered into the study database as follows:

- Complete clearance confirmed by investigator prior to Week 12
- Adverse Event (including LSRs deemed to be significant by investigator)
- Withdrawal of Consent by Subject/Caregiver
- Lost to Follow-Up
- Other

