10.3.3 Population Analysis

10.3.3.1 Disposition

Subject disposition information will be summarized for all subjects by treatment group. Summaries will include: the number of subjects screened, the number of subjects in each analysis population, the number of subjects where study treatment stopped, primary reason for study treatment stopped, the number of subjects completing 12 weeks of the study, the number of subjects completed the study, and the primary reason for discontinuation.

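### SAP 9.1 derives its 12-week study completion row from treatment completion, so subjects who stop drug for a reason other than clearance but stay through Week 12 are reported as not completing

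*SAP*

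**What the plan says.** Protocol 10.3.3.1 lists among its disposition summaries "the number of subjects completing 12 weeks of the study, the number of subjects completed the study". It attaches no treatment condition to either count, and treatment stopping is a separate item in the same list.

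SAP 9.1 supplies a definition. It counts "the number of subjects completing 12 weeks of the study (defined as having answered Yes to the question". The item in question, taken from the end-of-treatment page, is worded "Did the subject complete treatment through Week 12". The alternative to a Yes is that treatment ended early because of clearance. A further condition is that the subject "does not have a Study Exit date prior to the" Week 12 visit date.

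The protocol separates the two kinds of discontinuation:

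- Section 6.8.1, on drug stopped permanently for an adverse event: "the subject is discontinued from the treatment, but still participates in the study and the subject is encouraged to follow the visit schedule". It singles out the Week 12 and Week 24 assessments.
- Section 9.4: a subject found pregnant before Week 12 stops drug but continues visits through Week 24.
- Sections 6.8.2.2 and 6.8.3 give separate reason lists for stopping treatment and for leaving the study. "Complete clearance confirmed by investigator prior to Week 12" is on the treatment list only, next to adverse event, withdrawal of consent, loss to follow-up and other.

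SAP 14 declares no modification or clarification of the protocol's methods.

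**The concern.** The row is labelled as study completion but measures something closer to treatment completion. A subject who stops drug because of an application site reaction, stays in the study and has a lesion count at Week 12 has done what the protocol asks, yet falls outside the row.

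A row with this label is a natural place to look for retention to the time of the primary endpoint and for any difference between arms. Here it would mix tolerability with attrition. If drug is stopped for adverse events more often on SB206, as in the earlier studies, the row would show lower Week 12 retention on SB206 than actually occurred. It would also disagree with the other disposition rows and with the number of Week 12 lesion counts, and the report would not explain why.

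**Working it through.** **1. Does the subject fail the definition on every reading?** Let A = answered Yes on treatment completion, B = treatment ended for clearance, C = no Study Exit before the Week 12 visit. The sentence can be grouped as (A or B) and C, or as A or (B and C). A subject who stops for an adverse event and stays has A false, B false, C true. Both groupings give false. The same holds for pregnancy or any other reason except clearance. Condition C only removes subjects; it cannot bring this one back. Nor can the question be read loosely as asking about study participation, because the separate clearance route would then be unnecessary.

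**2. Inputs for size.** Protocol 2.1.4.2, Table 2, row "TEAE leading to study drug discontinuation" (Safety Population, through Week 24), and the planned 425 per arm (SAP 5).

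Reproducing the stated percentages:

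| Study | Vehicle | SB206 |
|---|---|---|
| NI-MC301 | 1/116 = 0.9% | 7/235 = 3.0% |
| NI-MC302 | 1/117 = 0.9% | 17/237 = 7.2% |

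All four agree with the table.

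**3. Pooling by arm.** SB206: (7 + 17)/(235 + 237) = 24/472 = 5.08%. Vehicle: (1 + 1)/(116 + 117) = 2/233 = 0.86%. At 425 per arm: 425 × 24/472 = 21.6 subjects and 425 × 2/233 = 3.6 subjects.

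**4. Understatement of 12-week study completion.** Let f be the share of these subjects who stay through Week 12. The documents give no value, so f is assumed to lie between 25% and 100% and to be equal in both arms. Understatement in points = f × rate; artificial gap = f × (5.08 − 0.86).

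| f | SB206 | Vehicle | Gap |
|---|---|---|---|
| 100% | 21.6 subjects, 5.1 points | 3.6 subjects, 0.9 points | 4.2 points |
| 75% | 16.2 subjects, 3.8 points | 2.7 subjects, 0.6 points | 3.2 points |
| 50% | 10.8 subjects, 2.5 points | 1.8 subjects, 0.4 points | 2.1 points |
| 25% | 5.4 subjects, 1.3 points | 0.9 subjects, 0.2 points | 1.1 points |

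With equal staying, the SB206 share of affected subjects is 5.08/(5.08 + 0.86) = 86%. If only 25% stayed on SB206 but all stayed on vehicle, the gap would shrink to 1.27 − 0.86 = 0.4 points.

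**5. Is the row used elsewhere?** The primary rule (Protocol 10.3.1) depends on the Week 12 count and on discontinuing the study. The missing-data analyses in SAP 10.4 and 11.1 depend on a missing Week 12 count or on dropout before Week 12. None refers to the 9.1 definition.

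**The case against.** The strongest defence is that little harm follows. SAP 9.1 itself also asks for treatment stops with reasons, study completers, and reasons for discontinuation both before Week 12 and overall, all by arm. A Week 12 lesion count that was not performed is named in SAP 9.5 as a possible significant deviation, and those deviations are tabulated by arm. A careful reader can therefore recover much of the true retention. This stands, and it limits the point to a mislabelled row; no data are lost. It does not make the row correct: the report would still carry a figure that its own neighbouring rows contradict.

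Three stronger readings are tempting.

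- A reader might infer that the definition distorts the primary or missing-data analyses. Step 5 shows that it does not: estimate, test and power are unchanged.
- A reader might take the gap to be 2 to 6 points. Those are the study-by-study figures (2.98 − 0.86 = 2.1 and 7.17 − 0.85 = 6.3) if every subject who stops for an adverse event stays. Nothing in the documents supports full staying. Protocol 7.2.5 points the other way for suspected allergic contact dermatitis: it has the Week 12/ET assessments done when drug is stopped, so some of these subjects may have no true Week 12 count.
- A reader might infer a matching error in the opposite direction, because a subject who stopped for clearance and then missed Week 12 has no visit date against which to compare a Study Exit date. The SAP does not say how that case is handled. A subject who has not exited may reasonably be regarded as still in the study, so this is an unspecified edge case and not a demonstrated miscount.

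A simple remedy also has a trap. SAP 7 treats a Week 12/ET form with no Study Exit form on the same date as a Week 12 visit. A subject assessed early under Protocol 7.2.5 who remains in the study could then count as a 12-week completer whatever the study day. The new definition therefore needs a day limit.

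**Conclusion.** The point holds as a reporting error in one descriptive row. As written, SAP 9.1 counts subjects who stop drug for a reason other than clearance and stay through Week 12 as not completing 12 weeks of the study, contrary to the protocol's separation of treatment and study discontinuation. The definitional part follows from the text and needs no assumption.

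The size is a projection. At pooled earlier rates the row understates completion by up to about 5.1 points on SB206 and 0.9 on vehicle, with an artificial gap of about 1.1 to 4.2 points for equal staying of 25% to 100%. This rests on adverse-event stops only, on rates from two earlier studies counted through Week 24, and on the assumed staying share. That most affected subjects would be on SB206 is likewise an expectation from those studies and cannot be stated as a fact about this trial.

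The correction is worth making because it is cheap and the row bears on retention to the primary time point. It does not call the efficacy conclusion into question.

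**What to change.** 1. In SAP 9.1, define completion of 12 weeks of the study as no Study Exit before Week 12 and a Week 12 visit dated within the SAP 7 Week 12 analysis window (Day 72 to 98), whatever the treatment status. The lower limit is what keeps out forms completed early. State how a subject who misses Week 12 but attends later is shown; under this definition that subject is not a 12-week completer.
2. Keep the present derivation as a separate row labelled *completed treatment through Week 12 or stopped for clearance*, and make the grouping of its conditions explicit.
3. Record the definition in SAP 14.
4. Reconcile Protocol 7.2.5 with Protocol 6.8.1 on when the Week 12/ET assessments are done after drug is stopped, since this decides which subjects have a true Week 12 count.

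The cost is SAP wording, one extra disposition row with its date check, and a clarification in the protocol or study manual. The end-of-treatment page, Study Exit form and visit dates are already collected, and SAP 7 already compares Week 12/ET visits with the Study Exit form. No efficacy analysis changes.

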### 9.2 Eligibility

A listing of subjects not fulfilling any eligibility criteria will be created.

### 9.3 Demographic and Baseline Characteristics

Demographic variables include age, sex, ethnicity, and race. Age will be calculated in years relative to the informed consent date.

Other baseline characteristics include lesion counts at baseline, site type (dermatologist vs other), number of sites and a breakdown of site type, number of randomly assigned subjects in household (1 subject vs 2 subjects), number of households and breakdown of household size, BOTE score at Baseline (no inflammation [BOTE=0] vs mild/moderate/severe/very severe inflammation [BOTE $\geq$ 1]), and age at and time since onset of symptoms of current molluscum episode. Descriptive statistics will be presented for ages and other continuous variables. Frequency counts and percentages will be presented for sex, ethnicity, race, and other categorical variables. Demographic and baseline characteristics will be summarized for the Safety, ITT, and PP Populations.

### 9.4 Extent of Exposure

Study drug exposure will be summarized for each treatment using the total number of applications, the duration of treatment, and the number of subjects requiring a treatment interruption and modification. Duration of treatment is defined as the last application date minus the first application date plus 1. A subject will be deemed to have a treatment interruption if there is at least 1 dose not applied due to investigator’s instruction and to have a treatment modification if there is at least 1 dose which was modified due to investigator instruction.

Study drug compliance will be summarized and calculated as follows:

Compliance [%] = (Actual applications applied)/(Planned applications) × 100, where

- Actual applications applied = Planned applications – the number of applications not applied by the subject which were not investigator instructed.
- Planned applications = Number of applications (days) planned up to the point of treatment discontinuation or date of Week 12 visit, whichever is later.

This implies that if a subject discontinues treatment prior to Week 12 due to complete clearance, then the number of applications takes this information into account and the subject is not penalized for having complete clearance.

Compliance will be further summarized into 2 groups:

1. Subjects who did not have any interruptions or modifications using the same formula as above, and
2. Subjects with modifications or interruptions. For these subjects, an adjusted compliance will be calculated in the following manner: the actual applications applied will be the same as above but the planned applications will exclude the number of doses which were not applied due to investigator's instruction.

Subjects who do not have any interruptions or modifications will have no doses not applied due to investigator's instruction and no doses modified due to investigator's instruction.

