	
Subjects or their caregivers will apply treatment once daily to all lesions identified at Baseline and new lesions that arise during treatment for a minimum of 4 weeks and shall continue unless otherwise instructed by the investigator up to 12 weeks. If the investigator determines all lesions are cleared at a visit, the investigator may instruct the subject to stop treatment. If treatment is stopped due to clearance, subjects will continue regularly scheduled visits through Week 24/ET2. Study drug will be dispensed through Week 12/ET1 in case of lesion recurrence between study visits. At each visit subsequent to stopping treatment due to clearance, the investigator will determine if new lesions have occurred since the last visit, and if so, the subject or caregiver will be instructed by the investigator to re-initiate treatment. If the subject or caregiver see new lesions or re-occurrence of lesions in between visits, they should treat these lesions until the next visit. No study drug is planned to be provided after the Week 12 visit.
 
The subject or caregiver will apply study drug to the individual lesions. Periocular lesions will be treated if the lesions are at least 2 cm from the edge of the eye.
 
Subjects will visit the clinic in person at Screening/Baseline, Week 2, Week 4 (unless visit is performed remotely), Week 8, Week 12, and Week 24. At Baseline, the investigator will perform in person lesion counts. Then, the subjects/caregivers will be instructed on how to participate in remote visits and practice the technology. Once the initial in person lesion count has been completed by the assessor, an additional count by the same investigator will be made utilizing the remote technology platform to serve as a training for future remote visit.
 
Subjects will be contacted via phone on Day 2 to collect subject information on early dose reactions. The Week 4 Visit may be performed remotely or as an in-clinic visit. At Weeks 16 and 20, subjects will be contacted via phone to capture information regarding MC recurrence and adverse events (AEs); at Week 24, the subject will be seen at the site for a final study visit to assess scarring, keloids, and MC recurrence. Subjects who discontinue the study prior to the Week 12 visit due to AEs or other reasons will be asked to complete the Week 12 visit assessments; this will

--	--

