6.8.2 Treatment Modifications, Interruptions, and Discontinuation

If a subject experiences an LSR (AE) for the first time, the investigator must confirm if treatment is needed, if a treatment modification (hold treatment for certain areas) is needed, and/or if a treatment interruption (discontinue treatment in all areas) is needed. If the investigator confirms treatment is needed, the subject can continue study treatment on all areas, hold treatment in certain areas, or interrupt treatment completely, and add non-medicated treatment such as petroleum gel as a concomitant medication. This option can be exercised at any point during the study as needed.

If no concomitant treatment is added, the investigator may choose to withhold study treatment on either specific areas (modification) or all areas (interruption) until the investigator confirms it is appropriate to continue. It is recommended to modify or interrupt treatment for 2-3 days before re-starting the study treatment; the investigator should use their discretion for when to reinstate treatment by discussing the status of the AE with the subject/caregiver to determine if the event is resolved or if continued modification/interruption of study treatment is necessary. The investigator will confirm when reintroduction of study treatment can occur. This option can be exercised at any point during the study as needed.

For more severe AEs, concomitant treatment such as corticosteroids can be added while withholding study treatment on specific areas (modification) or all areas (interruption) until the investigator confirms it is appropriate to continue with the study drug. Similar to the modifications and interruptions above, it is recommended to modify or interrupt treatment for 2-3 days before re-starting the study treatment; the investigator should discuss the status of the AE with the subject/caregiver to determine if the event is resolved or if continued modification/interruption of study treatment is necessary. The investigator will confirm when reintroduction of study treatment can occur. This option can also be exercised at any point during the study as needed.

After the resolution of the first LSR and reinitiation of treatment, if a more severe second LSR occurs, it is appropriate to suspect the cause is allergic contact dermatitis. Study treatment on all areas should be discontinued, and after resolution of the second LSR, patch testing is

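### SAP 9.4 defines a treatment interruption without regard to reason or duration, so read literally it counts stops for complete clearance and permanent stops as interruptions

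*SAP*

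**What the plan says.** SAP 9.4 (Extent of Exposure) lists, among the exposure summaries, "the number of subjects requiring a treatment interruption and modification". Its rule is: "A subject will be deemed to have a treatment interruption if there is at least 1 dose not applied due to" the investigator's instruction. It names no reason, no limit on duration and no requirement that dosing resume. The section closes by saying that subjects without interruptions or modifications have no instructed unapplied doses, so the rule admits no exceptions.

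For compliance, the same section defines planned applications as "Number of applications (days) planned up to the point of treatment discontinuation or date of Week 12 visit, whichever is later". Applications applied are the planned number minus "the number of applications not applied by the subject which were not investigator instructed". For a subject who stops before Week 12 because of clearance, it concludes that "the number of applications takes this information into account and the subject is not penalized for having complete clearance". Compliance is then split into subjects without any interruption or modification (group 1) and subjects with one (group 2). Group 2 gets an adjusted figure that removes instructed unapplied doses from the denominator.

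On clearance, the protocol synopsis says: "If the investigator determines all lesions are cleared at a visit, the investigator may instruct the subject to stop treatment". Protocol 4.1 and SAP 4 repeat this.

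Protocol 6.8.2 uses the term for managing a local skin reaction recorded as an AE: the investigator decides "if a treatment interruption (discontinue treatment in all areas) is needed". Section 6.8.2.1 describes temporary holds, with an adverse event as the reason given. Section 6.8.2.2, on permanent discontinuation, lists investigator-confirmed clearance before Week 12 as its own reason for stopping treatment.

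**The concern.** The SAP rule turns on who gave the instruction, while the protocol's use of the term turns on why dosing was held. Three kinds of event then fall into one count: temporary holds for tolerability, permanent stops directed by the investigator, and stops because the treatment has done its job. A reader who sees a number of subjects *requiring* an interruption will take it as a statement about how often dosing had to be held, and an unknown part of it would reflect clearance. If clearance is more frequent on SB206, as the trial hypothesises, part of any between-arm difference in that row would come from efficacy. The same flag decides which compliance group a subject is summarised in.

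**Working it through.** **Does the text reach clearance stops?** SAP 9.4 gives no figure for interruptions, so there is none to reproduce. The test is whether its own rules fit together for a cleared subject.

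Take a subject who applies every dose through Day 57 (Week 8 target), is found clear, is told to stop, and attends Week 12 on Day 85.

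- Planned applications, to the later of the stop and the Week 12 visit: 85.
- Unapplied: 85 − 57 = 28.
- Compliance = (planned − unapplied doses not instructed) / planned × 100.

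| Status of the 28 doses | Compliance | Agrees with no penalty for clearance? | Flagged as interrupted? |
|---|---|---|---|
| Instructed | 85/85 = 100% | Yes | Yes |
| Not instructed | 57/85 = 67% | No | No |

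With planned doses running to Week 12, the SAP's statement that clearance is not penalised holds only in the first row, and that row meets the interruption definition. The subject then enters group 2, where adjusted compliance is 85/(85 − 28) = 85/57 = 149%. The excess over 100% arises because the numerator already credits the instructed doses while the denominator removes them.

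**Permanent stops.** Protocol 6.8.1 keeps a subject whose treatment the investigator has ended in the study and on the visit schedule. The remaining doses to Week 12 are again planned, unapplied and instructed, so the flag applies there too.

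**Illustrative size.** Inputs:

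- Week 8 complete clearance (Protocol 2.1.4.3): NI-MC301 15.3% SB206, 10.3% vehicle; NI-MC302 13.9% SB206, 5.9% vehicle.
- Weights, the safety-population sizes in Protocol Table 2: SB206 235 and 237; vehicle 116 and 117.
- Planned size: 425 per arm (SAP 5).

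Pooled SB206 = (235 × 0.153 + 237 × 0.139)/472 = 14.6%.

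Pooled vehicle = (116 × 0.103 + 117 × 0.059)/233 = 8.1%.

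Subjects with a clearance stop = 425 × pooled rate × share told to stop. The documents do not give that share, so a range is shown.

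| Share told to stop (assumed) | SB206 | Vehicle | Gap |
|---|---|---|---|
| 100% | 62 | 34 | 28 subjects, 6.5 points |
| 50% | 31 | 17 | 14 subjects, 3.3 points |
| 25% | 16 | 9 | 7 subjects, 1.6 points |

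**The case against.** The strongest reply is that the fault lies in one word of the planned-applications rule. If *later* was meant to be *earlier*, planned doses end at the stop, compliance is 57/57 = 100%, no planned dose is missed and nothing is flagged. The 149% figure makes a slip there plausible. The documents also separate the concepts elsewhere: Protocol 6.8.2.2 and SAP 9.1 treat clearance as an end-of-treatment reason, and Protocol 8.6 speaks of investigator-instructed interrupted or modified doses in a way that fits the 6.8.2 holds.

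This has force as a guess at intent, but it is not what is written, and the interruption sentence is not itself confined to planned doses. It is also incomplete. Protocol 4.1, 4.3 and 8.2 let a cleared subject resume treatment on recurrence. A subject who stops on instruction and later restarts has an instructed gap inside the treatment period and is flagged under either wording, though fewer subjects would be affected.

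The objection on importance stands. A reader might infer that this row is the trial's main measure of tolerability; it is not. It is one item in Table 14.1.3.1 (Study Drug Exposure). TEAEs leading to drug discontinuation, LSR scores and events of special interest are reported separately, and the disposition table gives the primary reason treatment stopped.

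A reader might also take the 100% row as an upper bound. It is not: single-visit Week 8 rates omit subjects who cleared and were stopped earlier and then recurred. Conversely, some cleared subjects will also have had an AE hold and would be flagged anyway. Comparing these counts with the earlier rates of TEAE-led discontinuation would not help, because those are not interruption rates.

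**Conclusion.** The point holds as a defect of definition. Applied literally, SAP 9.4 merges clearance stops and permanent investigator-directed stops with the temporary AE and skin-reaction holds that the protocol calls interruptions, and it assigns those subjects to compliance group 2. The consequence is limited to a descriptive exposure count and a compliance grouping; no efficacy analysis uses the flag.

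The size cannot be fixed from the documents. It depends on how often investigators use an optional instruction, and on Week 8 clearance resembling the earlier studies. A reader might conclude that the count will be inflated more on SB206. The documents support that only as an expectation, from the trial's hypothesis and from higher Week 8 clearance on SB206 in both earlier studies. The eCRF and table shells are not among the documents and might distinguish the reasons, but the SAP does not tell the programmer to use such a distinction.

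**What to change.** In SAP 9.4:

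1. Reserve *interruption* for temporary investigator-instructed holds for any reason other than complete clearance. Restricting it to AE, LSR or intolerability would go too far, because it would drop other instructed holds such as the one for suspected pregnancy in Protocol 9.4.
2. Report clearance stops and permanent discontinuations as separate rows, and show holds by reason where the database records it. Clearance stops should include those followed by a restart, which the end-of-treatment reason alone may not identify.
3. Use the same definition for compliance group 2, and amend the section's closing sentence, which equates having no interruption with having no instructed unapplied doses.
4. At the same time, reconcile the end point of planned applications with the statement about clearance, and correct the adjusted formula so that it cannot exceed 100%.

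Items 1 to 3 cost SAP wording and one derivation, made before unblinding; item 4 adds a correction to the compliance formula. One check is needed first. Protocol 6.8.2.1 requires the hold reason in source documents, whereas 6.8.2.2 puts the end-of-treatment reason in the database. Confirm that the hold reason is also in the database, for example in the data behind Listing 16.2.5.3 (Dosing Plan and Treatment Modification).
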